2.0 STUDY RATIONALE

As previous trials with eryaspase evidenced promising overall safety and activity profiles, the current study is thus set out by NOPHO (the sponsor) to evaluate the PK/PD and safety of eryaspase at the dose of 150 IU/kg in combination with multi-agent chemotherapy, as a promising alternative option to allow ALL patients who have exhibited hypersensitivity reactions with pegylated E.coli L-asparaginase formulation (clinical allergy or silent inactivation) to maximize the delivery of planned asparaginase therapy.

2.1 Risk / Benefit Assessment

2.1.1 Potential Benefit for the Patients

PEG-asparaginase in combination with polychemotherapy is used in consolidation, delayed intensification, and maintenance phases of ALL treatment, mainly in children and young adults. However, its use has been hampered by frequent and/or significant toxicities, of which immunologic reactions take a prominent place. In addition, loss of enzymatic efficacy, the so called "silent inactivation" may be observed as a consequence of the production of symptom-free serum antibodies directed to the asparaginase moiety and blocking its pharmacological activity.

Eryaspase has been proposed as a new approach to maintain an activity of L-asparaginase while reducing its antibody mediated toxicity and improve its safety profile. Eryaspase at a dose of 150 IU/kg of L-asparaginase, according to previous study designs in combination with standard chemotherapy, was shown to be effective and well tolerated in children and adults with relapsed ALL (17) or in elderly (23). Previous study showed that eryaspase efficacy/safety profile of both doses 100 and 150 IU/Kg achieved sustained asparaginase activity with no excessive limiting toxicities.

This trial will explore the tolerability and the biological activity of eryaspase in patients with previous hypersensitivity to PEG-asparaginase formulation. The expected benefit for those patients is to provide them an additional alternative therapy with eryaspase.

This Nordic Society of Pediatric Haematology and Oncology (NOPHO) protocol NOR-GRASPALL 2016 is a Multi-agents protocol with eryaspase expected to be as effective as NOPHO ALL 2008 and ALLTogether pilot protocol Multi-agents protocol with pegylated E.coli L- asparaginase and better tolerated.

2.1.2 Potential Risks for the Patients

Adverse effects resulting from the administration of asparaginase or erythrocytes are well known. Toxicity data come from clinical studies carried on since 2005 with eryaspase as add-on therapy with protocols combining several chemotherapies that have their own toxicity profile.

In study GRASPALL 2009-06, the incidence of allergic reactions was in both eryaspase arms in the non-allergic (7.7%) and allergic patients (11.5%). There were no withdrawals due to hypersensitivity reactions, either in the allergic or non-allergic patient subsets. The most common drug-related events with eryaspase were hypofibrinogenemia (26.9%), asymptomatic pancreatitis (26.9%), elevated transaminases (19.2%), hypoalbuminemia (15.4%), and decreased anti-thrombin III (11.5%).

The risk of asparaginase related toxicities is not increased compared to the treatment with other formulations of asparaginase e.g. PEG-asparaginase.

Detailed safety information is summarized in the Investigator Brochure.

The risk of transfusion complications are very low when national guidelines for blood transfusions are followed, the risk rate is 3.7/100000 transfusions of red blood cells which include transfusion with incorrect blood components.(24)

The patients will not have any inconvenience and risk because of extra hospital visits, blood tests, lumbar punctures for CSF collecting and clinical assessments because it all will be done according to the conventional investigations in the NOPHO ALL 2008 or ALLTogether pilot protocol.

Previous studies have shown a good safety profile and the risk of toxicity is not increased compared to the conventional treatment with PEG-asparaginase. According to that it is assessed that getting eryaspase and completing the asparaginase treatment are beneficial compared to the risk. The risk is considered reasonable in proportion to the severity of the diagnosis and the conventional treatment according to the NOPHO ALL 2008 or ALLTogether pilot protocol.

3.0 STUDY OBJECTIVES

3.1 Primary Objective

Main objectives of this study are to evaluate the pharmacological (pharmacokinetic and pharmacodynamic) profile of eryaspase administered to patients who experience PEG-asparaginase hypersensitivity event during induction, consolidation or subsequent phases of the multi-agent chemotherapy in NOPHO ALL 2008 or ALLTogether pilot protocol for the treatment of children and adult patients with ALL;

The pharmacological profile of eryaspase, determined by:

- The pharmacokinetic (PK) parameters for asparaginase activity will be assessed: C_{max} ; T_{max} ; AUC (Area Under the Curve); $T_{1/2}$ (half-life); V_{ss} (Distribution Volume at steady state), MRT (Mean Residence Time) and CL (Clearance).

- The pharmacodynamic (PD) parameters for cerebrospinal fluid (CSF) concentrations of asparagine, aspartate, glutamine, and glutamate will be assessed.

3.2 Secondary Objectives

- To assess the immunogenicity of eryaspase as determined by assessment of anti-L-asparaginase antibodies and neutralizing antibodies.
- To assess the overall safety and tolerability of eryaspase in combination with multi-agent NOPHO ALL 2008 chemotherapy according to the PdL toxicity consensus definitions for asparaginase related toxicities (hypersensitivity, pancreatitis, hyperlipidemia, SOS, thrombosis, osteonecrosis, and fungal infections)(25).
- Evaluate the effect of Eryaspase on the concurrent maintenance therapy with 6-mercaptopurine and methotrexate. Levels of cytotoxic methotrexate (MTX polyglutamates) and 6-mercaptopurine metabolites (6-thioguanine nucleotides, 6TGN, and methylated metabolites, MeMP) and of DNA-TGN levels in circulating leukocytes.

3.3 Exploratory Objective

- The pharmacodynamic (PD) parameters for plasma and whole blood: Concentration of asparagine, aspartate, glutamine, and glutamate will be assessed.

4.0 CRITERIA FOR EVALUATION

4.1 Primary Endpoints

The study endpoints are to evaluate:

Pharmacokinetic parameters:

- Total-activity (at time points listed in Section 8.4.1) will be measured. The main pharmacokinetic parameters will be assessed: Cmax; Tmax; T1/2 (half-life time); Vss (Distribution Volume at steady state), MRT (Mean Residence Time) and clearance.
- Percentage of patients with continuous asparaginase activity >100 IU/L.
- Duration of enzyme activity >100 IU/l at 6 w dosing intervals

Pharmacodynamic profile:

- CSF concentrations of amino-acids: (asparagine, aspartate, glutamine, glutamate), at time points listed in the Study Procedures and Guidelines section.

Immunogenicity: titers of anti-asparaginase antibodies and neutralizing antibodies.

Safety: Incidence of hypersensitivity (allergic reactions, any grade, and silent inactivation) at the end of asparaginase treatment

All parameters that will be taken account are those defined in the Study Procedures and Guidelines section.

4.2 Secondary Endpoints

The secondary endpoints are to evaluate:

- The safety and tolerability of eryaspase in combination with standard multi-agent NOPHO ALL 2008 or ALLTogether pilot protocol chemotherapy assessed during eryaspase treatment period according to potential toxicities defined in the Adverse Experience section.
- Toxicity of the eryaspase treatment compared to the conventional PEG-asparaginase treatment. Toxicity and SAE's will be evaluated according to the PdL toxicity consensus definitions.
- Levels of maintenance metabolites

4.3 Exploratory Endpoint

- Plasma and whole blood concentrations of amino acids: asparagine, aspartate, glutamine, glutamate. Time points listed in the study Procedures and Guidelines section.

4.4 Safety Evaluations

All AEs/SAEs will be collected at start of treatment until 30 days after last administration.

SAE's will be registered according to the NOPHO ALL 2008 or ALLTogether pilot protocol toxicity registration and classified and described according to the PdL consensus paper on ALL treatment related toxicity(1).

[figure not shown]

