TEST PRODUCT, DOSE, AND ROUTE OF ADMINISTRATION	
Eryaspase will be administered intravenously (IV) at a dose of 150 IU/kg every 2 weeks for a maximum of 4 doses and then for a maximum of 3 doses at 6-week intervals for patients treated in the NOPHO 2008 protocol. For patients in the ALLTogether pilot protocol Eryaspase will be administered intravenously (IV) at a dose of 150 IU/kg every 2 weeks for a maximum of 7 doses.
 
Eryaspase will substitute remaining doses of PEG-asparaginase according to the NOPHO ALL 2008 or ALLTogether pilot protocol.

CONTROL PRODUCT, DOSE AND ROUTE OF ADMINISTRATION	None.
DURATION OF SUBJECT PARTICIPATION AND DURATION OF STUDY	
Subjects will be on study for approximately 1.5 years including follow-up.
 
Screening: up to 8 days
 
Treatment: approximately 6 months
 
Follow-up: Primary trial assessments for each patient will continue for 1 month following the end of planned eryaspase treatment phases. Each patient will be followed for up to one (1) year maintenance follow-up as defined in the NOPHO ALL 2008 protocol or ALLTogether pilot protocol. Each patient will receive cytostatic treatment in about 22 months after last administration of eryaspase according to the NOPHO ALL 2008 protocol. Follow-up after cessation should be done according to guidelines on each country and site and includes no assessments for this study.
 
Patient enrolment will start in Denmark in January 2017. It is estimated that up to 50 patients could be enrolled by the end of February 2020. The total duration of the study is expected to be 4 years. 3 years for subject recruitment and 1 year for final subject follow-up.

CONCOMITANT MEDICATIONS	
Allowed: Standard therapy for ALL is allowed except for treatments noted in the exclusion criteria described above and as noted in the prohibited medications section below.
 
Blood transfusions, antibiotic therapy, and other form of supportive care are allowed.
 
Prohibited:
 
 • Concomitant vaccination with live vaccines as it may increase the risk of serious infection • Other L-asparaginase marketed products • Highly hemolytic agents that may lead to RBCs hemolysis: Acetanilide, Antipyrine Phenazone, and Chloroquin and derivatives 
NOTE: Benzodiazepine may be given if indicated.

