Asparaginase has a central part of the treatment of childhood ALL. Asparaginase is an enzyme that hydrolyses asparagine to aspartic acid and ammonia and, to some extent, glutamine to glutamic acid and ammonia (4). In the extra cellular space this results in asparagine depletion and a reduction of glutamine. The lymphoblasts, which cannot effectively synthesize *de novo* asparagine, have their protein biosynthesis inhibited, and they undergo apoptosis (5). Cerebrospinal fluid (CSF) asparagine depletion is considered as a marker of asparaginase effect in the central nervous system (CNS) and asparaginase play an important role in CNS-directed anti-leukemia therapy(6).

In the current NOPHO ALL 2008 protocol, PEG-asparaginase (pegylated E.coli asparaginase) is for non-high risk (non-HR) patients given from treatment week 5 to 35, being given at a dose of 1000 IU/m² i.m. every two weeks. Children and adults (aged 1-45 years) in five Nordic and two Baltic countries (Lithuania and Estonia) are treated according to ALL2008. HR patients receive PEG-asparaginase once at the end of induction, once in each HR treatment block (7-9 blocks) and twice during DI. From January 2009 until March 2016 at treatment day 92 (after 5 doses of PEG-asparaginase at 2 weeks intervals) non-HR Nordic children (85% of all Nordic children with ALL) were offered a randomization

between continuous and intermittent PEG-asparaginase treatment (given every 2nd or every 6th weeks, respectively).

The randomization was closed March 1st 2016 and non-HR patients are now treated according to the previous experimental arm (i.e. PEG-asparaginase every 6w from day 92). Manuscript of the results of the randomization is in preparation.

In ALLTogether pilot protocol PEG-asparaginase (1500 I.E./m² i.v. <16 years, and 1000 I.E./m² i.v. ≥16 years) is given from treatment day 4 and repeated at 2-week intervals. The non-high risk group consists of three treatment groups after stratification day 29, i.e. very-low risk, intermediate low risk and intermediate high risk and receiving 4, 5 and 8 doses, respectively. Therapeutic drug monitoring are done routinely to identify enzyme inactivation (silent or in combination with hypersensitivity reactions). Optimization of asparaginase treatment is considered one of the major focus areas in the ALLTogether protocol.

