The use of PEG-asparaginase are compromised by frequent and significant toxicities, such as clinical allergic reactions, pancreatitis, and thrombosis. Clinical allergy is the most frequent serious adverse event observed. In total, 13% of the patients (~30/year) treated on the NOPHO ALL 2008 protocol develop allergy to PEG-asparaginase (7). The majority (85%) of the Nordic ALL2008 childhood ALL patients who developed allergy, did so after the 2nd or 3rd dose and are thus potentially undertreated because further doses are impossible.

Truncated asparaginase therapy is associated with inferior event-free survival outcomes, in particular CNS relapse. It is well known that insufficient CSF asparagine depletion is a concern and is correlated with ineffective killing of leukemic cells in the CNS. CNS may serve as a sanctuary for leukemic cells, and consequently this may increase the risk of CNS relapse despite other CNS-directed therapy. Truncated L-asparaginase treatment has been associated with increased risk of CNS relapse (8-10).

The impact of asparaginase truncation due to clinical allergy may depend on the timing of the allergic event (10). Data from NOPHO ALL 2008 protocol (manuscript in preparation) indicates that there retrospectively is no asparaginase-activity from start of treatment in patients who later develop clinical allergy. This means that patients with hypersensitivity reactions have no effect of the treatment with asparaginase at all.

In addition, loss of enzymatic efficacy - "silent inactivation" are found in 5-6% of the patients who receive conventional PEG-asparaginase treatment. It is observed as a consequence of the production of symptom-free serum antibodies directed to the asparaginase and blocking its pharmacological activity. These patients have no effect of the asparaginase treatment as well. (Manuscript in preparation).

After an allergic reaction, non-HR patients are treated with Erwinase (20.000 IU/m² 3 times a week for two weeks) during Delayed Intensification, and HR patients during the subsequent blocks and DI. Erwinase has a short half-life (7-16 hrs), thus frequent administration is necessary. There is a need for an effective alternative preparation with a longer half-life for PEG-asparaginase allergic patients. In the current NOPHO ALL 2008, protocol PEG-asparaginase treatment is only replaced for 2 weeks and further scheduled doses are cancelled. The importance of the treatment with asparaginase is so

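### Osteonecrosis is a named, graded safety toxicity, but it is tabulated only to 30 days after the last eryaspase dose; one item in the existing maintenance follow-up would describe later cases cheaply

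*Protocol*

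**What the plan says.** **Objective and definition.** Protocol 3.2 sets out to assess safety against consensus definitions for "asparaginase related toxicities (hypersensitivity, pancreatitis, hyperlipidemia, SOS, thrombosis, osteonecrosis, and fungal infections". Table 3 gives osteonecrosis four grades, asks for MRI confirmation, and notes that it can go on to joint-surface collapse and arthritis.

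**Window.** Protocol 4.4 states: "All AEs/SAEs will be collected at start of treatment until 30 days after last administration". Protocol 10.0 and SAP 2.4.4 set the same limit, and SAP 8.1 ends the treatment period for its treatment-emergent tables 30 days after the last eryaspase dose. The first safety endpoint in Protocol 4.2 is "assessed during eryaspase treatment period according to potential toxicities defined in the Adverse Experience section".

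**Time on study.** The synopsis says "Subjects will be on study for approximately 1.5 years including follow-up". Protocol 8.1 follows patients for up to one year of maintenance. Protocol 8.3.2 has monthly metabolite samples in the first maintenance year, with blood counts and liver tests at the same times and maintenance details entered in the CRF. Protocol 11.1 asks patients who stop eryaspase early to continue assessments to the same point. No osteonecrosis item is assigned to that year.

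**Recording rules.** Protocol 10.0 keeps events unrelated to eryaspase off the CRF, and the synopsis collects only potentially related ones. Protocol 10.2 requires every Table 3 toxicity on the CRF, with no such filter. SAP 8.1 makes its primary adverse event presentation irrespective of causality. The same SAP section also says events are collected until 30 days after eryaspase or chemotherapy, whichever that proves to be, and that all of them are listed.

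**The concern.** A toxicity singled out in the objective is tabulated over a window whose length depends on how many eryaspase doses a patient happens to receive. It then drops out of the tables while the patient is still seen monthly for this study. Because Table 3 says the condition can progress, both its occurrence and its grade could change after the cut-off. At stake is a description of osteonecrosis over the follow-up that the trial already runs.

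The recording conflict matters even inside the window. Two sites with the same case could handle it differently: one omits it as unrelated under Protocol 10.0, the other records it under Protocol 10.2. A table meant to ignore causality cannot recover events that never reached the CRF.

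**Working it through.** The plan states no figure for the length of the safety window, so it is built from the dosing schedules.

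**Formula.** Window = days from first to last eryaspase dose + 30.

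**Inputs.**
- NOPHO PEG-asparaginase: day 92 falls "after 5 doses of PEG-asparaginase at 2 weeks intervals", followed by six-weekly dosing (Protocol 1.0). Eryaspase: at most 4 two-weekly doses, then at most 3 six-weekly doses (Protocol 7.4.2).
- The gap between the last two-weekly and the first six-weekly dose is not stated. It is taken as 14 or 42 days.
- ALLTogether: two-weekly dosing, with risk groups "very-low risk, intermediate low risk and intermediate high risk and receiving 4, 5 and 8 doses, respectively".
- Timing of reactions: "The majority (85%) of the Nordic ALL2008 childhood ALL patients who developed allergy, did so after the 2nd or 3rd dose". This covers NOPHO children only; applying it to ALLTogether is an assumption.

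**Results (planned courses).**

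| Situation | Calculation | Window (days) |
|---|---|---|
| Single dose, either protocol | 0 + 30 | 30 |
| NOPHO, seven doses | 42 + 14 or 42 + 84 + 30 | 170 or 198 |
| NOPHO, reaction to PEG dose 2 | 28 + 14 or 42 + 84 + 30 | 156 or 184 |
| NOPHO, reaction to PEG dose 3 | 14 + 14 or 42 + 84 + 30 | 142 or 170 |
| ALLTogether very low risk, reaction to dose 3 or 2 | 0 or 14, + 30 | 30 or 44 |
| ALLTogether intermediate-low, same | 14 or 28, + 30 | 44 or 58 |
| ALLTogether intermediate-high, same | 56 or 70, + 30 | 86 or 100 |

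So most allergic NOPHO children would have a planned window of 142-184 days. Short windows come from late reactions, the two lower ALLTogether risk groups, or early stopping. Protocol 7.6 stops eryaspase for allergy of any grade, pancreatitis, serious haemorrhage or thrombosis, or absent activity.

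**Share of time on study.** 1.5 years is about 548 days. For seven NOPHO doses, 170/548 = 31% and 198/548 = 36%. For shorter courses the share depends on when the maintenance year starts relative to the last dose, which is not stated.

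**The SAP collection sentence.** Protocol 5.1 has chemotherapy continuing for about 22 months after the last eryaspase dose. Read literally, the SAP would collect events for about 22 × 30.4375 + 30 = 700 days after that dose, against 30 in the protocol. Cases after day 30 would appear in listings but not in the tables.

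**Precision.** With zero events the exact two-sided 95% upper limit is 1 − 0.025^(1/n). For n = 50 (protocol) it is 7.1%; for n = 55 (SAP 4.1) it is about 6.5%.

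**The case against.** The strongest reply is that the endpoint and the window agree. Protocol 4.2 confines the first safety endpoint to the eryaspase treatment period, and the objective promises no long-term incidence. That stands: the on-treatment rate is valid and should be kept.

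A second reply is that serious cases are not abandoned. Protocol 10.4.1 follows every SAE to recovery, stabilisation, sequelae or death with no 30-day limit, and persistent disability is a seriousness criterion in 10.1. This also stands, and it narrows the gap to new late onset and non-serious progression. Protocol 4.4 sends SAEs to the parent protocol's toxicity registration as well, but neither document plans to bring later registry cases into this analysis.

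A third reply is that longer follow-up says little about eryaspase in a single-arm trial after PEG-asparaginase with continuing chemotherapy. That is true, and it is why only a descriptive result is proposed.

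A reader might infer that the reported percentage would be presented as study-long incidence. The documents do not support this: SAP 2.4.4 and 8.1 state the window, and the table shells are in a separate document. A reader might also turn to the endpoint "Toxicity of the eryaspase treatment compared to the conventional PEG-asparaginase treatment". How that comparison would be made is a separate question, and this point does not rest on it.

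**Conclusion.** An optional, low-cost improvement, not an error in the on-treatment endpoint. Osteonecrosis is tabulated for 30 days after a single dose and for about 170-198 days after seven NOPHO doses, while patients remain in study follow-up for up to a year of maintenance. The day counts assume planned courses and a 14- or 42-day switch between intervals.

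It is tempting to conclude that cases will be missed. The documents do not show this. They give no onset times, the 31-36% is a share of calendar time rather than of events, and the undercount may be zero. Nor do they show that all recording ceases at 30 days, given the SAE follow-up rule and the SAP's reference to chemotherapy.

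Two inconsistencies hold whatever view is taken of longer follow-up: the relatedness filter in Protocol 10.0 and the synopsis against the Table 3 rule in 10.2, and the end of collection in the protocol against SAP 8.1.

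**What to change.** 1. State in Protocol 10.0 that Table 3 toxicities, including osteonecrosis, are recorded regardless of attributed relatedness, so that 10.2 governs over 10.0 and the synopsis and agrees with SAP 8.1.
2. Keep the 30-day window for adverse events generally, and align the SAP 8.1 collection sentence with the protocol.
3. Add one osteonecrosis item (onset date, Table 3 grade) to the maintenance CRF through the existing follow-up of up to one year. Report a separate descriptive cumulative incidence from first eryaspase dose, censored at last follow-up, outside the treatment-emergent tables.

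**Cost.** One clarifying sentence in the protocol, one aligned sentence in the SAP, one CRF item and one SAP table, with no new visit or imaging.

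**Downsides.** Late cases reflect the whole regimen and cannot be attributed to eryaspase alone. Asymptomatic cases are missed because no MRI is scheduled. Counts will be small, and even zero events would leave the upper limits shown above.
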